3.3.2.5 Days 5-7

- Review of medications and supplements;
- Measurement of vital signs (weight, seated SBP/DPB, and heart rate);
- Provide a dose of study treatment or placebo at approximately 7am (\pm 60 minutes);
- Provide breakfast no sooner than 45 minutes after the morning dose;
- Provide a dose of study treatment or placebo at approximately 1pm (\pm 60 minutes);
- Provide lunch no sooner than 45 minutes after the afternoon dose;
- Provide dinner at approximately 7pm (\pm 60 minutes);
- Provide a dose of study treatment or placebo at approximately 10pm (\pm 60 minutes);
- Continue CGM monitoring;
- Adverse events will be monitored and recorded.

3.3.2.6 Day 8

- Review of medications and supplements;
- Measurement of vital signs (weight, seated SBP/DPB, and heart rate);
- Provide a dose of study treatment or placebo at approximately 7am (\pm 60 minutes);
- Provide breakfast no sooner than 45 minutes after the morning dose;

- Provide a dose of study treatment or placebo at approximately 1pm (\pm 60 minutes);
- Provide lunch no sooner than 45 minutes after the afternoon dose;
- Provide dinner at approximately 7pm (\pm 60 minutes);
- Provide a dose of study treatment or placebo at approximately 10pm (\pm 60 minutes);
- Collect a blood sample according to schedule (per randomization scheme, either morning, afternoon, or evening) prior to the specified dose of placebo for:
 - Pre-dose PD analysis
 - Serum chemistry
- Collect scheduled (per randomization scheme) postdose PD blood draws every 30 minutes (\pm 5 minutes) until 5 hours has elapsed;
- Continue CGM monitoring;
- Adverse events will be monitored and recorded.

3.3.2.7 Day 9

- Review of medications and supplements;
- Measurement of vital signs (weight, seated SBP/DPB, and heart rate);
- Provide a dose of single-blind placebo at approximately 7am (\pm 60 minutes);
- Provide breakfast no sooner than 45 minutes after the morning dose;
- Provide a dose of single-blind placebo at approximately 1pm (\pm 60 minutes);
- Provide lunch no sooner than 45 minutes after the afternoon dose;
- Provide dinner at approximately 7pm (\pm 60 minutes);
- Provide a dose of single-blind placebo at approximately 10pm (\pm 60 minutes);
- Continue CGM monitoring;
- Adverse events will be monitored and recorded.

3.3.2.8 Day 10

- Review of medications and supplements;
- Measurement of vital signs (weight, seated SBP/DPB, and heart rate);
- Remove the CGM monitor; download CGM data;
- Provide breakfast;
- Adverse events will be monitored and recorded.

- Subjects will be discharged for a minimum 2-week washout period.

3.3.3 Period 3

Subjects will report to the CRU on the morning of Day 1.

3.3.3.1 Day 1

- Review of medical history;
- Review of medications and supplements;
- Measurement of vital signs (weight, seated SBP/DPB, and heart rate);
- Provide the first dose of single-blind placebo at least 45 minutes prior to breakfast;
- Provide breakfast;
- Subjects will be fitted with the continuous glucose monitoring (CGM) device and data recording will begin;
- Provide 4 doses of single-blind placebo and instruct subjects to take one dose at least 45 minutes before lunch, one dose at bedtime, one dose at least 45 minutes before breakfast on Day 2, and one dose at least 45 minutes before lunch on Day 2.
- Adverse events will be monitored and recorded.
- Subjects will be instructed to return to the CRU at approximately 5pm (± 30 minutes) on Day 2.

3.3.3.2 Day 2

- Admission to the CRU at approximately 5pm (± 30 minutes);
- Review of medications and supplements;
- Measurement of vital signs (weight, seated SBP/DPB, heart rate, and temperature);
- Perform breathalyzer;
- Collect a urine sample for:
 - Drug screen;
 - Pregnancy testing (WCBP only)
- Provide a standardized diabetic meal at approximately 7pm (± 60 minutes). Standardized meals will continue throughout the remainder of the study Period.
- Provide a dose of single-blind placebo at approximately 10pm (± 60 minutes).
- Continue CGM monitoring;
- Adverse events will be monitored and recorded.

3.3.3.3 Day 3

- Review of medications and supplements;
- Measurement of vital signs (weight, seated SBP/DPB, heart and rate);
- Provide a dose of single-blind placebo at approximately 7am (\pm 60 minutes);
- Provide breakfast no sooner than 45 minutes after the morning dose;
- Provide a dose of single-blind placebo at approximately 1pm (\pm 60 minutes), at least 45 minutes prior to lunch;
- Provide lunch no sooner than 45 minutes after the afternoon dose;
- Provide dinner at approximately 7pm (\pm 60 minutes);
- Provide a dose of single-blind placebo at approximately 10pm (\pm 60 minutes);
- Collect a blood sample according to schedule (per randomization scheme, either morning, afternoon, or evening) prior to the specified dose of placebo for:
 - Pre-dose PD analysis
 - Serum chemistry
- Collect scheduled (per randomization scheme) postdose PD blood draws every 30 minutes (\pm 5 minutes) until 5 hours has elapsed;
- Replace the CGM cannula at approximately 7pm (\pm 60 minutes), such that it does not interfere with any post-dose PD blood draws;
- Adverse events will be monitored and recorded.

3.3.3.4 Day 4

- Review of medications and supplements;
- Measurement of vital signs (weight, seated SBP/DPB, and heart rate);
- Randomization
- Provide a dose of study treatment or placebo at approximately 7am (\pm 60 minutes);
- Provide breakfast no sooner than 45 minutes after the morning dose;
- Provide a dose of study treatment or placebo at approximately 1pm (\pm 60 minutes), at least 45 minutes prior to lunch;
- Provide lunch no sooner than 45 minutes after the afternoon dose;
- Provide dinner at approximately 7pm (\pm 60 minutes);
- Provide a dose of study treatment or placebo at approximately 10pm (\pm 60 minutes);

- Continue CGM monitoring;
- Adverse events will be monitored and recorded.

3.3.3.5 Days 5-7

- Review of medications and supplements;
- Measurement of vital signs (weight, seated SBP/DPB, and heart rate);
- Provide a dose of study treatment or placebo at approximately 7am (\pm 60 minutes);
- Provide breakfast no sooner than 45 minutes after the morning dose;
- Provide a dose of study treatment or placebo at approximately 1pm (\pm 60 minutes);
- Provide lunch no sooner than 45 minutes after the afternoon dose;
- Provide dinner at approximately 7pm (\pm 60 minutes);
- Provide a dose of study treatment or placebo at approximately 10pm (\pm 60 minutes);
- Continue CGM monitoring;
- Adverse events will be monitored and recorded.

3.3.3.6 Day 8

- Review of medications and supplements;
- Measurement of vital signs (weight, seated SBP/DPB, and heart rate);
- Provide a dose of study treatment or placebo at approximately 7am (\pm 60 minutes);
- Provide breakfast no sooner than 45 minutes after the morning dose;
- Provide a dose of study treatment or placebo at approximately 1pm (\pm 60 minutes);
- Provide lunch no sooner than 45 minutes after the afternoon dose;
- Provide dinner at approximately 7pm (\pm 60 minutes);
- Provide a dose of study treatment or placebo at approximately 10pm (\pm 60 minutes);
- Collect a blood sample according to schedule (per randomization scheme, either morning, afternoon, or evening) prior to the specified dose of placebo for:
 - Pre-dose PD analysis
 - Serum chemistry
- Collect scheduled (per randomization scheme) postdose PD blood draws every 30 minutes (\pm 5 minutes) until 5 hours has elapsed;
- Continue CGM monitoring;

- Adverse events will be monitored and recorded.

3.3.3.7 Day 9

- Review of medications and supplements;
- Measurement of vital signs (weight, seated SBP/DPB, and heart rate);
- Provide a dose of single-blind placebo at approximately 7am (\pm 60 minutes);
- Provide breakfast no sooner than 45 minutes after the morning dose;
- Provide a dose of single-blind placebo at approximately 1pm (\pm 60 minutes);
- Provide lunch no sooner than 45 minutes after the afternoon dose;
- Provide dinner at approximately 7pm (\pm 60 minutes);
- Provide a dose of single-blind placebo at approximately 10pm (\pm 60 minutes);
- Continue CGM monitoring;
- Adverse events will be monitored and recorded.

3.3.3.8 Day 10

- Review of medications and supplements;
- Measurement of vital signs (weight, seated SBP/DPB, and heart rate);
- Remove the CGM monitor; download CGM data;
- Provide breakfast;
- Adverse events will be monitored and recorded.
- Subjects will be discharged until the 1-week follow-up visit.

3.4 Follow-up Visit (Visit 3, 7 to 9 Days after the end of Visit 2, Period 3)

Subjects will return to the clinic 7 to 9 days after Visit 2/Day 10 (approximately 65 days since the beginning of the study) and the following procedures will be performed:

- Review of medications and supplements;
- Vital signs (including weight, seated SBP/DPB, and heart rate);
- Physical examination;
- Collection of blood and urine samples for:
 - Clinical safety labs, including hematology, serum chemistry, and urinalysis (see Section 6.3.5 for list of tests);

- Record adverse events;
- Discharge from the study.

Any subject with a possible study treatment related AE at the Follow-Up Visit will be followed until resolution or stabilization of the event. Further, any SAE, whether or not related to study treatment, that occurs within 30 days following the last dose of study treatment will be followed until resolution or stabilization of the event. This may require additional clinical assessments and laboratory tests. The follow-up results will be recorded in the subject's source documentation and in the CRF.

3.5 Early Withdrawal (EW)

If a randomized subject is withdrawn from the study prior to completing study treatment, the subject will be discharged from the CRU and instructed to return to the clinic the next day and the following procedures will be performed:

- Review of medications and supplements;
- Vital signs (including weight, seated SBP/DPB, and heart rate);
- Physical examination;
- Collection of blood and urine samples for:
 - Clinical safety labs, including hematology, serum chemistry, and urinalysis (see Section 6.3.5 for list of tests);
- Record adverse events;
- Discharge from the study.

If a randomized subject is withdrawn from the study prior to completing all three treatment periods, the subject will be discharged from the CRU and instructed to return to the clinic the next day for Follow-Up evaluations as performed for Visit 3.

Any subject with a possible study treatment related AE at the time of EW will be followed until resolution or stabilization of the event.

3.6 Schedule of Events

Table 1 below describes the daily schedule of events from Screening Visit 1 through Follow-Up Visit 3.

Table 1: Daily Schedule of Events from Screening Through Follow-Up Visit

Visit	Screening Visit 1	Treatment Visit 2 Periods 1, 2, and 3										Follow-Up Visit 3	EW		
		Study Day	Day -7 to -10	1	2	3	4	5	6	7	8			9	10
Informed Consent	X														
Medical History	X	X													
Demographics	X														
Concomitant Medications	X	X	X	X	X	X	X	X	X	X	X	X	X	X	X
Inclusion/Exclusion Criteria	X														
Physical Exam	X												X	X	
ECG	X														
Vital Signs ¹	X	X	X	X	X	X	X	X	X	X	X	X	X	X	
Hematology/Chemistry/Urinalysis ²	X ²			X ²						X ²			X ²	X ²	
Urine Drug Screen	X		X												
Breathalyzer	X		X												
Serum Pregnancy Test ³	X														
Urine Pregnancy Test ³			X												
Placebo Administration ⁴		X	X	X							X				
CGM Monitoring ⁵		X	X	X	X	X	X	X	X	X	X				
CRU Admission			X												
Standardized Diabetic Meals ⁶		X	X	X	X	X	X	X	X	X	X				
Pharmacodynamic Samples ⁷				X					X						
Remove CGM and Download Data											X				
Randomization/Crossover ⁸					X										
Treatment Administration ⁹					X	X	X	X	X						
CRU Discharge											X				
Adverse Events		X	X	X	X	X	X	X	X	X	X	X	X	X	
Study Disposition												X	X		

- ¹Vital signs include height, weight, heart rate, systolic BP, and diastolic BP. Height will be measured at Screening only. Temperature will be measured at Visit 2/Day 2 only, prior to admission.
- ²Screening labs will include standard hematology/chemistry/urinalysis, plus HbA_{1c}, C-peptide, and TSH. FSH will also be performed for women who are pre-menopausal. On Visit 2 Days 3 and 8, chemistry analysis will be performed without hematology or urinalysis. Visit 3 and EW labs will include standard hematology/chemistry/urinalysis.
- ³Pregnancy tests will be performed for women of childbearing potential only.
- ⁴A single dose of placebo will be administered on the morning of Day 1. Subjects will be dispensed the next 4 doses (8 capsules) with dosing instructions. On Day 3 and Day 9, doses will be administered at approximately 7am (±60 minutes), 1pm (±60 minutes), and 10pm (±60 minutes).
- ⁵The CGM monitor will be fitted on Day 1, the cannula will be changed on Day 3 at approximately 7pm (±60 minutes), and the monitor will continue recording measurements until the morning of Day 10.
- ⁶A standardized breakfast will be provided on Day 1. Beginning with dinner on Day 2 and ending with breakfast on Day 10, breakfast and lunch will be provided no sooner than 45 minutes after corresponding treatment doses. Dinner will be provided at approximately 7pm (±60 minutes). Standardized snacks will be provided between breakfast and lunch, between lunch and dinner, and between dinner and bedtime.
- ⁷Blood samples (scheduled per randomization scheme) for insulin and C-peptide will be drawn pre-dose and every 30 minutes (± 5 minutes) postdose until 5 hours has elapsed.
- ⁸Randomization will occur on the morning of Period 1/Day 4. Crossover will occur on the morning of Period 2/Day 4 and then again on the morning of Period 3/Day 4.
- ⁹Subjects will receive their assigned randomized treatment from the morning of Day 4 through the evening of Day 8. Doses will be administered at approximately 7am (±60 minutes), 1pm (±60 minutes), and 10pm (±60 minutes).

4 STUDY SUBJECT SELECTION

4.1 Inclusion Criteria

Each subject must meet all of the following criteria to be eligible for the study:

1. Male or female subjects, age 20 to 75 years, inclusive with type 2 diabetes mellitus.
2. At Visit 2/Period 1/Day 1, subjects will have been treated for their diabetes by metformin (≥ 1000 mg/day; any type and regimen), metformin and a DPP-4 inhibitor, metformin and an SGLT-2 inhibitor, metformin and TDZ, or metformin and sulfonylurea. Subjects will have been on a stable regimen of metformin (defined as the same metformin dose and type) and other treatments for at least 8 weeks prior to Visit 2/Period 1/Day 1.
3. Body Mass Index (BMI) between 25 and 40 kg/m², inclusive, at Screening.
4. Hemoglobin A1c (HbA_{1c}) between ≥ 7.5 and $\leq 10.5\%$ at Screening.
5. Fasting serum glucose greater than or equal to 126 mg/dL at Screening.
6. Females of childbearing potential must have a negative serum pregnancy test result at Screening and a negative urine pregnancy test at Visit 2/Day 1 for all study Periods.
 - a. Females who are not of childbearing potential are defined as:
 - i. Postmenopausal (defined as at least 12 months with no menses in women ≥ 45 years of age)
 - ii. Has had a hysterectomy and/or bilateral oophorectomy, bilateral salpingectomy, or bilateral tubal ligation/occlusion at least 6 weeks prior to screening; OR
 - iii. Has a congenital or acquired condition that prevents childbearing.
 - b. Females of childbearing potential agree to avoid becoming pregnant while receiving study treatment and for 14 days after the last dose of study treatment by complying with one of the following:
 - i. practice abstinence[†] from heterosexual activity OR
 - ii. Use (or have her partner use) acceptable contraception during heterosexual activity. Acceptable methods of contraception are[‡]:
 1. Single method (one of the following is acceptable):
 - a. Non-hormonal intrauterine device (IUD)
 - b. vasectomy of a female subject's male partner
 2. Combination method (requires use of two of the following):
 - a. diaphragm with spermicide (cannot be used in conjunction with cervical cap/spermicide)
 - b. cervical cap with spermicide (nulliparous women only)
 - c. contraceptive sponge (nulliparous women only)
 - d. male condom or female condom (cannot be used together)

†Abstinence (relative to heterosexual activity) can be used as the sole method of contraception if it is consistently employed as the subject's preferred and usual lifestyle and if considered acceptable by local regulatory agencies and ERCs/IRBs. Periodic abstinence (e.g., calendar, ovulation, sympto-thermal, post-ovulation methods, etc.) and withdrawal are not acceptable methods of contraception.

‡If a contraceptive method listed above is restricted by local regulations/guidelines, then it does not qualify as an acceptable method of contraception for subjects participating at sites in this country/region.

4.2 Exclusion Criteria

Subjects who meet any of the following criteria must be excluded from the study:

1. Usage of anti-diabetic agents other than metformin, sulfonylurea, SGLT-2 inhibitors, TZD, or DPP-4 inhibitors within 6 weeks prior to Visit 2/Period 1/Day 1.
2. Presence of any clinically significant endocrine disease according to the Investigator (euthyroid subjects on replacement therapy will be included if the dosage of thyroxine is stable for at least six weeks prior to Screening).
3. Clinical diagnosis of type 1 diabetes.
4. Fasting serum glucose >300 mg/dL at Screening; a single repeat test is allowable.
5. Evidence of unawareness of hypoglycemia, a documented plasma glucose ≤ 50 mg/dL in the absence of symptoms of hypoglycemia at Screening.
6. Presence of any clinically significant condition (in the opinion of the Investigator) that might interfere with the evaluation of study medication, such as significant renal, hepatic, gastrointestinal (GI), cardiovascular (CV), immune disease, blood dyscrasias or any disorders causing hemolysis or unstable red blood cells, or clinically important hematological disorders (i.e. aplastic anemia, myeloproliferative or myelodysplastic syndromes, thrombocytopenia) at Screening.
7. Presence or history of cancer within the past 5 years of Screening, with the exception of adequately-treated localized basal cell skin cancer or in situ uterine cervical cancer.
 - a. A subject with a history of malignancy >5 years prior to Screening should have no evidence of residual or recurrent disease.
 - b. A subject with a history of melanoma, leukemia, lymphoma, or renal carcinoma is excluded.
8. Laboratory abnormalities at Screening including:
 - a) C-peptide < 1.0 ng/mL
 - b) Positive pregnancy test in females of childbearing potential (at Screening and Visit 2/Periods 1-3/Day 1)
 - c) Abnormal serum thyrotropin (TSH) levels below the lower limit of normal or $>1.5X$ the upper limit of normal
 - d) Elevated liver enzymes (alanine transaminase (ALT), alanine aminotransferase (AST), alkaline phosphatase) $>2X$ the upper limit of normal.
 - e) Very high triglyceride levels (>600 mg/dL); a single repeat test is allowable.

- f) Any relevant abnormality that would interfere with the efficacy or the safety assessments during study treatment administration.
9. Positive history of active liver disease (other than non-alcoholic hepatic steatosis), including chronic hepatitis B or C, primary biliary cirrhosis, or active symptomatic gallbladder disease.
10. Positive history of HIV.
11. Use of the following medications:
 - a) History of use of insulin for more than 1 week within 6 months prior to and none within 6 weeks prior to Visit 2/Period 1/Day 1.
 - b) History of use of aprotinin at any time prior to Screening (e.g., Trasylol, any type or dose).
 - c) Administration of thyroid preparations or thyroxine (except in subjects on stable replacement therapy) within 6 weeks prior to Screening.
 - d) Administration of systemic long-acting corticosteroids within two months or prolonged use (more than one week) of other systemic corticosteroids or inhaled corticosteroids (if daily dosage is > 1,000 µg equivalent beclomethasone) within 30 days prior to Screening. Intra-articular and/or topical corticosteroids are not considered systemic.
 - e) Use of medications known to modify glucose metabolism or to decrease the ability to recover from hypoglycemia such as oral, parenteral, and inhaled steroids (as discussed above), and immunosuppressive or immunomodulating agents.
12. Known allergy to soy or aprotinin.
13. Subject is on a weight loss program and is not in the maintenance phase, or subject has started weight loss medication (e.g., orlistat or liraglutide), within 8 weeks prior to Screening. Subjects who have had bariatric surgery are also excluded.
14. Subject is pregnant or breast-feeding.
15. Subject has a Screening systolic blood pressure ≥ 165 mmHg or diastolic blood pressure ≥ 100 mmHg. Subjects will be allowed to take a BP rescue medication.
16. Subject is a user of recreational or illicit drugs or has had a recent history (within 1 year of Screening) of drug or alcohol abuse or dependence. (Note: Alcohol abuse includes heavy alcohol intake as defined by >3 drinks per day or >14 drinks per week, or binge drinking) at Screening.
17. Any clinically significant ECG abnormality at Screening or cardiovascular disease. Clinically significant cardiovascular disease will include:
 - a) History of stroke, transient ischemic attack, or myocardial infarction within 6 months prior to Screening,
 - b) History of or currently have New York Heart Associate Class II-IV heart failure prior to Screening, or
18. One or more contraindications to metformin.
19. History of gastrointestinal disorders (e.g. hypochlorhydria) with the potential to interfere with drug absorption.

20. At the Principal Investigator's discretion, any condition or other factor that is deemed unsuitable for subject enrollment into the study.

4.3 Subject and Trial Discontinuation

Subjects may choose to withdraw from this study at any time for any reason without penalty of jeopardizing their health care or loss of benefits to which the subject is otherwise entitled.

Within the provisions of informed consent and good clinical judgment with respect to safety, every attempt will be made to have subjects complete the study. The following are reasons to terminate a subject's participation in the study:

1. Subject experiences an AE that in the judgement of the Investigator poses a significant risk to the subject for continued participation in the study.
2. Subject uses a prohibited medication (listed in Section 5.7) that in the judgment of the Investigator poses a significant risk to the subject for continued participation in the study or that will interfere with the interpretation of the results of the study.
3. Subject becomes pregnant.
4. Significant protocol violation or noncompliance on the part of the subject or the Investigator.
5. Intercurrent illness that requires treatment that is not consistent with the protocol requirements, or intercurrent illness or the associated treatment that in the judgment of the Investigator poses a significant risk to the subject for continued participation in the study.
6. Subject wishes to withdraw for any reason.
7. Sponsor elects to end the study, or the Investigational Site elects to end the study at their site.
8. Any other reason that in the judgment of the Investigator poses unacceptable risk to the subject.

Reasons for study drug discontinuation may include the following:

1. Pregnancy
2. Adverse event
3. Episodes of hypoglycemia as defined in Section 7.3.1.
4. Patient meets one of the exclusion criteria during the study
5. Any clinically significant change in the patient's medical condition

The occurrence of severe hypoglycemia (as defined in Section 7.3.1) in two patients during the double-blind treatment period will lead to unblinding of the treatment in those two patients.

Patients who withdraw from the study prior to treatment may be replaced. Patients who are withdrawn and have received at least one treatment will not be replaced. Patients who discontinue study drug treatment will not be replaced.

Except in cases of emergency, the Investigator should consult with the Sponsor and the Medical Monitor before removing the subject from the study. In some circumstances it may be necessary to temporarily interrupt treatment as a result of AEs that may have an unclear relationship to study treatment. The Investigator should obtain approval from the Sponsor and Medical Monitor before restarting study treatments that were temporarily discontinued for an AE.

In the event that a subject discontinues the study prior to completion, the date the subject is withdrawn and the reason for discontinuation will be recorded in the source documents and CRF. Although a subject will not be obliged to give his/her reason for withdrawing prematurely, the Investigator will make a reasonable effort to obtain the reason while fully respecting the subject's rights.

All subjects who are randomized and treated (i.e., received any amount of study treatment) will be included in the safety analyses. Thus, every effort will be made to contact any subject who fails to attend any follow-up appointments/contacts, in order to ensure that he/she is in satisfactory health. If a subject withdraws from the study as a result of meeting discontinuation criteria after the start of study treatment administration, reasonable efforts should be made to have the subject return for the early withdrawal evaluations (Section 3.5). Any subject withdrawn due to a suspected study treatment -related AE should be followed until resolution or stabilization of the event.

If a subject becomes pregnant, study treatment will be discontinued immediately, and the subject will be referred to an obstetrician/gynecologist experienced in reproductive toxicity for further evaluation and counseling. The subject will be followed until delivery or other termination of pregnancy for outcome.

Subjects may choose to withdraw authorization to use and disclose their PHI as defined by the HIPAA. Such withdrawal of authorization must be made to the Investigator in writing. Any PHI collected by the Investigator prior to the date of such withdrawal will continue to be used and disclosed.

Randomized subjects who are discontinued from this study for any reason will not be replaced.

The Sponsor has the right to terminate this study, and the Investigator/Investigational Site has the right to close the site, at any time, although this should occur only after consultation between involved parties. The Investigator will notify the IRB in writing of a premature termination of a study or closure of Investigational Site, and will send a copy of the notification to the Sponsor.

Events that may trigger premature termination of a study or closure of an Investigational Site include, but are not limited to, a new toxicity finding, a request to discontinue the trial from a regulatory authority, non-compliance with the protocol, GCP violations, slow recruitment/low enrollment, or change in development plans for the study treatment.

If either of the criteria listed below is met, enrollment of new subjects and dosing of ongoing subjects will be temporarily stopped. The Investigator, Sponsor, and the Medical Monitor will discuss whether a lower dose or any additional treatment guidelines should be implemented, or if the trial should be permanently stopped. Any proposed changes to the protocol to address such findings will be submitted for review and approval by the IRB and FDA prior to re-starting the trial.

1. A death within 30 days after study treatment administration where there is a reasonable possibility that the drug caused the event;
2. Two Grade 4 AEs where there is a reasonable possibility that the study treatment caused the events.

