3 INVESTIGATIONAL PLAN

3.1 Overall Study Design and Plan

This study will enroll approximately 30 adult subjects with T2DM from age 20 to 75 inclusive. Following a 7-10 day Screening period, eligible subjects will enter a 3-day single-blind placebo run-in. On Day 4, each subject will be randomized to a treatment sequence that will include three treatment assignments for each of three treatment Periods according to the randomization scheme. All subjects will receive placebo plus two of the following: ORMD-0801 460 IU **qd**, ORMD-0801 **bid**, or ORMD-0801 **tid**. Subjects will receive the randomized treatment from Day

4 through Day 8. A 24-hour single-blind placebo washout will be done on Day 9. For all treatment Periods, pre-treatment CGM data will be collected for approximately 36 hours prior to treatment (Days 1-3). The cannula will be changed and the monitor will remain in place throughout the 5-day treatment period (Days 4-8) and for an additional 24 hours post-treatment (Day 9). Blood samples for PD analysis will be taken pre-treatment (Day 3) and at end of treatment (Day 8) to check for concentrations of insulin and C-peptide in the blood. In addition, adverse events, clinical laboratory values, vital signs, and electrocardiograms (ECGs) will be evaluated periodically for safety. Subjects will be discharged on the morning of Day 10. Each treatment Period will be separated by a 2-week washout. A final follow-up visit will be performed 1 week after the end of the third treatment period.

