7.3.1 Adverse Events of Hypoglycemia

The CTCAE (version 4.0) definition for mild, moderate, and severe hypoglycemia based on blood glucose will be used, as shown below:

Mild: from 55 to <70 mg/dL (3.0 to < 3.8 mmol/L)

Moderate: from 40 to < 55 mg/dL (2.2 to < 3.0 mmol/L)

Severe: from 30 to < 40 mg/dL (1.7 to < 2.2 mmol/L)

Life Threatening: < 30 mg/dL (< 1.7 mmol/L)

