2.7. Safety Evaluations

2.7.1. Adverse Events

Adverse events will be coded using the Medical Dictionary for Drug Regulatory Affairs (MedDRA) version 16.0 and tabulated, including categorical information of interest such as onset and resolution times, time of onset relative to dose, severity at onset, maximum severity, causal relationship to study medication, and action taken. The severity of AEs will be graded according to NCI CTCAE version 4.03.

Treatment-emergent adverse events (TEAEs) are defined as any AE that starts or increases in severity after the first randomized dose of study treatment on visit 2/Day 4. The incidence of TEAEs will be tabulated by MedDRA preferred term, system organ class, treatment group, severity, and assigned relationship to study treatment. Adverse events will also be summarized by severity and relationship to the investigational product (IP).

The incidence of serious AEs, drug-related AEs, serious and drug-related AEs, and any AEs resulting in discontinuation from the study will be listed.

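### Minor: the two-patient unblinding trigger names only severe hypoglycemia (30 to <40 mg/dL), so an event classed below 30 mg/dL does not literally count toward it

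*Protocol*

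**What the plan says.** Protocol Section 4.3 contains a mandatory rule: "severe hypoglycemia (as defined in Section 7.3.1) in two patients during the double-blind treatment period will lead to unblinding of the treatment". The action is confined to the patients who triggered it: the events "will lead to unblinding of the treatment in those two patients". The same section lists "Episodes of hypoglycemia as defined in Section 7.3.1" among the possible reasons for stopping study drug. It also pauses enrollment and dosing after two Grade 4 adverse events that the study treatment may have caused.

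Section 7.3.1 supplies the definition that the rule points to. Its lead-in names three classes: "The CTCAE (version 4.0) definition for mild, moderate, and severe hypoglycemia based on blood glucose will be used". Four classes follow. The two that matter here are "Severe: from 30 to < 40 mg/dL (1.7 to < 2.2 mmol/L" and "Life Threatening: < 30 mg/dL (< 1.7 mmol/L", both printed with a closing parenthesis.

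Three other places bear on the point:
- Section 7.4.2 directs that the blind be broken for a subject with a medical emergency, or with a serious event that is unexpected and possibly related.
- Section 3.1 says of the continuous glucose monitor (CGM) that "the monitor will remain in place throughout the 5-day treatment period (Days 4-8".
- SAP Section 2.7.1 tabulates, among other items, "severity at onset, maximum severity, causal relationship to study medication".

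**The concern.** The parenthesis in the Section 4.3 rule imports a definition, so the ordinary sense of the word severe does not govern. The imported definition has a floor at 30 mg/dL. Read literally, a patient whose event falls in the class below that floor does not add to the count of two, and the rule can stop applying as events get worse.

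What is at stake is whether a stated safety rule acts when it was meant to. No estimate, test or sample-size figure depends on it.

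**Working it through.** No figure in the plan needs to be reproduced. The check applies the Section 4.3 rule to the Section 7.3.1 classes.

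**Inputs**
- Trigger: at least 2 patients with severe hypoglycemia (Section 4.3).
- Severe: 30 to <40 mg/dL. Life-threatening: <30 mg/dL (Section 7.3.1).
- How a patient is assigned to a class: not stated for this rule. The greatest-severity rule in Protocol Section 8.4.2 is for summary tables. SAP Section 2.7.1 tabulates two severities per event, but it governs reporting, not unblinding during the trial. SAP Section 2.7.2 reports hypoglycemia by class without an assignment rule.

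Two assignment rules are therefore tried: the lowest reading, and any recorded reading of 30 to <40.

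**Step 1: is the trigger met?** The illustrative readings are in mg/dL. Each cell gives the number of patients counted.

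| Patient A; patient B | Lowest reading | Any reading of 30 to <40 | Trigger reworded to <40 |
|---|---|---|---|
| 35; 35 | 2, met | 2, met | 2, met |
| 35; 25 only | 1, not met | 1, not met | 2, met |
| 25 only; 25 only | 0, not met | 0, not met | 2, met |
| 45, 36, 28; 50, 34, 27 | 0, not met | 2, met | 2, met |

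Under the lowest-reading rule, every <30 patient drops out of the count. Under the any-reading rule, a <30 patient drops out only if no value of 30 to <40 was recorded. A pair at 35 and 36 counts 2 under either rule.

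**Step 2: who is still blinded after Section 7.4.2?** Patients are classed by lowest reading. Each <30 event is taken to be handled as a medical emergency, and the severe event is not.
- Severe + severe: the trigger is met, so 2 − 2 = 0 remain blinded.
- Severe + <30: the trigger is not met and the code break covers the <30 patient, so 2 − 1 = 1 remains blinded, the severe patient.
- <30 + <30: the trigger is not met and the code break covers both, so 2 − 2 = 0 remain blinded.

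**Step 3: does the Grade 4 pause close the gap?** Section 7.6 gives life-threatening events Grade 4, so by its label the <30 class maps to Grade 4. A severe + <30 pair supplies one such event, and the pause needs two. A <30 + <30 pair supplies two. If both are judged possibly related, the pause applies, although that rule does not itself call for unblinding.

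**The case against.** The strongest reply is that Section 4.3 does not class patients at all. It asks whether severe hypoglycemia occurred in two patients. With a glucose monitor worn throughout Days 4-8, a patient who falls below 30 mg/dL would often have a recorded value of 30 to <40 on the way down. That patient would then count, and the gap closes. This stands as a limit on how often the problem could arise. It does not settle the wording, because the protocol never says that any reading in the band suffices, and the gap remains where no such value is recorded.

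Second, the intent is fairly clear. The lead-in to Section 7.3.1 names three classes while four are listed, which suggests that severe was meant to take in anything worse. That is probably right. But a mandatory rule with an explicit cross-reference should not depend on staff looking past the definition it cites. Section 7.6 also keeps the two levels apart, with severe at Grade 3 and life-threatening at Grade 4.

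Third, the worst events have stronger rules of their own: the individual code break, the Grade 4 pause and discontinuation of study drug. This stands, and it sets the size of the point. A reader might infer that patients below 30 mg/dL would be left blinded with no safety response, or that both members of a pair would stay blinded. The documents do not support that. Section 7.4.2 makes the code break mandatory in a medical emergency and needs no second patient. Leaving two patients blinded would require a <30 mg/dL event not to be treated as an emergency.

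Finally, the rule already accepts that a lone severe patient stays blinded. That is true, but in a 35 and 25 pair the severe patient is not alone in any clinical sense.

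**Conclusion.** The point holds and is minor. It is a defect in the lower bound of a safety threshold. A reader might infer that the rule excludes every patient who falls below 30 mg/dL, but that is too strong: the exclusion depends on classing by lowest reading, which the documents do not state, or on the absence of any recorded value of 30 to <40.

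The residual gap is one patient, the severe member of a severe plus <30 mg/dL pair. This assumes that the <30 event is handled as a medical emergency and the severe event is not. If the severe event were also treated as an emergency, the gap would be zero. The documents give no event rates, so no probability can be attached. Missing the trigger changes neither dosing nor enrollment, since its only action is to unblind two patients, and no endpoint or analysis is affected.

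**What to change.** In the Section 4.3 rule, replace the reference to severe hypoglycemia with *severe or life-threatening hypoglycemia (<40 mg/dL, as defined in Section 7.3.1)* and leave the rest of the sentence as it is. A patient has some reading below 40 exactly when the lowest reading is below 40, so the single threshold also removes the question of which reading counts. No further sentence is needed, because nothing in Section 4.3 suggests that this rule and the Grade 4 pause displace each other.

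The cost is one phrase in a protocol amendment. Endpoints, sample size and analysis do not change.
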